**Clinical Study Protocol**  
**Johnson & Johnson Vision Care, Inc.**

Visit 2: Treatment 1 Follow-Up (after two weeks)		
Step	Procedure	Details
2.7	Subjective comfort	
Subjective comfort scores using a vertical VAS scale will be recorded for the following for each lens (OD and OS):
 
Comfort just after lens application over the two week period
 
Comfort just before lens removal over the two week period

2.8	LogMAR visual acuity & over-refraction	Distance high contrast visual acuity will be measured for each eye and binocularly before and after over-refraction.
2.9	Lens fitting and surface assessment	
Lens fit will be recorded for each of the following criteria: horizontal centration, vertical centration, movement and coverage.
 
The lens surface will be recorded according to the following integer scales: lens deposits (0-2), deposit degree (0-4), lens debris (0-4) and lens wettability (0-4).

2.10	Lens removal	Lenses will be removed and discarded.
2.11	Confocal microscopy (ONLY subjects who are classified as asymptomatic or symptomatic)	
Confocal microscopy will be undertaken in the following areas:
 
OD and OS Central upper lid margin
 
OD and OS Central lower lid margin
 
A number of images will be undertaken across the central lid area. Image analysis will be subsequently undertaken in order to determine the number of white blood cells.

2.12	Slit lamp biomicroscopy	
Grades will be scored to the nearest 0.1 in the best judgment of the investigator using Efron Grading Scales.
 
N.B. For subjects who are NOT classified as asymptomatic or symptomatic slit lamp biomicroscopy will take place as part of the final evaluation form.

2.13	Continuance	
For a subject to continue on the study they must meet the following criteria:
 
Their CLDEQ-8 score must be either <math>\leq 10</math> (to be classified as asymptomatic)

**Clinical Study Protocol**  
**Johnson & Johnson Vision Care, Inc.**

Visit 2: Treatment 1 Follow-Up (after two weeks)			
Step	Procedure	Details	
		
or <math>\geq 20</math> (to be classified as symptomatic).
 
Subjects who discontinue from the study at this stage should complete an exit form (a copy is given) as well as a final evaluation form.
 
Reimbursement issued for discontinuing subjects.
	
2.14	Exit Visual Acuity	Record distance high contrast logMAR visual acuity (OD, OS and OU) with their refractive correction from Part 1, Visit 1 (or habitual spectacles) in place.	Eurolens Research SOP # 12a
2.15	End of Visit 2 and Instructions	Continuing subjects will be asked to return for Visit 3 between 2 and 180 days after Visit 2, and may resume use of their habitual contact lenses until then. Subjects should be asked NOT to wear their lenses to Visit 3.	

**PART 1, VISIT 3**

Visit 3 will take place in the morning and subjects MUST attend without lenses *in situ*. If possible subjects should not wear lenses for 24 hours prior to the study visit in order to reduce the risk of biomicroscopic signs being a cause of being unable to continue on the study.

If subjects attend wearing their own lenses, this visit should NOT go ahead. The visit can still go ahead if the subject has worn their habitual lenses in the 24 hours prior to the visit.

Visit 3: Baseline			
Step	Procedure	Details	
3.1	Adverse Events and Concomitant Medications Review	Review any changes to the subject's medical history or concomitant medications from the previous study visit. Record any changes, and any adverse events.	
3.2	Subjective comfort	Subjective comfort scores using a vertical VAS scale will be recorded for each eye separately before lens application.	
3.3	Entrance Visual Acuity	Record distance high contrast LogMAR visual acuity (OD, OS and OU) with their refractive correction from Part 1, Visit 1 (or habitual spectacles), in place.	Eurolens Research SOP # 12a

**Clinical Study Protocol**  
**Johnson & Johnson Vision Care, Inc.**

Visit 3: Baseline			
Step	Procedure	Details	
3.4	Tear meniscus height	
The OD lower tear meniscus will be imaged using the OCT.
 
Three images will be taken.
	Eurolens Research SOP # 58
3.5	Non-invasive tear break-up time	
OD tear film break up time will be measured using the Medmont topographer
 
Three measurements will be undertaken.
	Eurolens Research SOP # 16
3.6	Tear film osmolarity	
OD osmolarity measured using the Tearlab.
 
Two measurements will be undertaken.
	Eurolens Research SOP # 52
3.7	Tear sample collection	
OD; 2<math>\mu</math>l tear sample will be collected using a capillary glass tube before application of any dyes to the ocular surface.
 
Tears will be collected over a maximum period of 15 minutes.
	Eurolens Research SOP # 57
3.8	Slit lamp biomicroscopy (white light only)	
Grades will be scored to the nearest 0.1 in the best judgment of the investigator using Efron Grading Scales for both eyes.
 
OS: NO LID EVERSION
	Eurolens Research SOP #13
3.9	Continuance	
If any slit lamp findings are Efron Grade 3 or greater (e.g. corneal oedema, corneal neovascularization, tarsal abnormalities, conjunctival injection) or < Efron Grade 3 which in the investigator's opinion would contraindicate contact lens wear, the subject may not continue at this time.
 
If in the opinion of the investigator the subject may be eligible at a later date, the subject may be brought in for up to ONE additional visit of this type.
	

Visit 3: Treatment 2 Lens Fitting and dispensing			
Step	Procedure	Details	
3.10	Ocular surface and lid margin staining photography and grading	
OS ONLY: Sodium fluorescein will be added to the ocular surface and the following will be graded using Efron scales: corneal and bulbar conjunctival staining.
	Eurolens Research SOP #13

**Clinical Study Protocol**  
**Johnson & Johnson Vision Care, Inc.**

Visit 3: Treatment 2 Lens Fitting and dispensing		
Step	Procedure	Details
		
OS ONLY: Lissamine green will then be added to the ocular surface and photographs of the upper and lower lid margin staining will be taken. These images will be used to subjectively grade lid margin staining at the time of the visit and for subsequent automated image analysis.
 
OS: after all lissamine green assessments have been completed, the eyelid will be everted and the palpebral conjunctiva will be graded using Efron Grading scales.

3.11	Lens application	
A Dailies AquaComfort Plus contact lens will be applied to each eye (lens selection based on BVP worn between Visits 1-2). BVP and lot number will be recorded. If a lens is damaged, a Product Quality Complaint Form will be completed. The lens will be stored in a labeled vial with unpreserved saline, and clearly differentiated from any other lenses.
 
Lenses will settle for 5 minutes

3.12	Subjective comfort	Subjective comfort scores for each lens (OD and OS) separately using a vertical VAS scale will be recorded.
3.13	LogMAR visual acuity & over-refraction	
Distance high contrast visual acuity will be measured for each eye and binocularly before and after over-refraction. The acuity will be recorded to the nearest letter for each eye.
 
If there is an over-refraction of +/- 0.50DS or more, the lenses would usually be changed. However, the final decision on this will rest with the investigator. Up to TWO power modifications are allowed.
 
If the lens is changed, the lens application, comfort and VA steps should be repeated.
 
N.B. Minimum acceptable logMAR VA is 0.18 binocularly.

**Clinical Study Protocol**  
**Johnson & Johnson Vision Care, Inc.**

Visit 3: Treatment 2 Lens Fitting and dispensing			
Step	Procedure	Details	
3.14	Lens fitting and surface assessment	
Lens fit will be measured using a slit lamp graticule for the following:
 
Coverage:            Nasal coverage            Temporal Coverage            Inferior Coverage            Superior Coverage
 
Centration:            Horizontal centration (by auto calculation)            Vertical centration (by auto calculation)
 
Movement in primary position
 
The lens surface will be recorded according to the following integer scales: lens deposits (0-2), deposit degree (0-4), lens debris (0-4) and lens wettability (0-4).
	Eurolens Research SOP # 24
3.15	Tear meniscus height	
The OD lower tear meniscus will be imaged using the OCT.
 
Three images will be taken.
	Eurolens Research SOP # 58
3.16	Non-invasive tear break-up time	
OD tear film break up time will be measured using the Medmont topographer
 
Three measurements will be undertaken.
	Eurolens Research SOP # 16
3.17	Tear film osmolarity	
OD osmolarity measured using the Tearlab.
 
Two measurements will be undertaken.
	Eurolens Research SOP # 52
3.18	Tear sample collection	
OD; 2<math>\mu</math>l tear sample will be collected using a capillary glass tube before application of any dyes to the ocular surface.
 
Tears will be collected over a maximum period of 15 minutes.
	Eurolens Research SOP # 57
3.19	LogMAR visual acuity	
Distance high contrast visual acuity will be measured for each eye and binocularly. The acuity will be recorded to the nearest letter for each eye.
	Eurolens Research SOP # 12a

**Clinical Study Protocol**  
**Johnson & Johnson Vision Care, Inc.**

Visit 3: Treatment 2 Lens Fitting and dispensing		
Step	Procedure	Details
3.20	Dispensing criteria	
The lens fit and VA must be acceptable in order for a subject to be able to continue on the study.
 
Since no other base curves are available, if the lens fit is deemed to be inadequate the subject should be exited from the study.
 
Minimum acceptable logMAR VA is 0.18 binocularly
 
If subject is deemed to be unable to continue, proceed to the Final Evaluation and complete all forms.

3.21	Lens wear instructions	The subject will be instructed to wear the lenses for the rest of the day and not to remove the lenses before the next visit.
3.22	End of Visit 3 and Instructions	Subject discharged and asked to return $14 \pm 2$ hours later (from the time of lens application).

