**Clinical Study Protocol**  
**Johnson & Johnson Vision Care, Inc.**

PART 1				
Visit	1	2	3	4
	Screening, Baseline, Treatment 1	Treatment 1 Follow- up	Treatment 2	Treatment 2 Follow-up
Time Point		14 ± 3 days from Visit 1  6±1 hours lens wear on visit day	2 to 180 days from Visit 2	14 ± 2 hours from Visit 3
Estimated Visit Duration	1.5 hours	1.5 hours	3.0 hours	2.0 hours
Statement of Informed Consent/Privacy statement	X			
Demographics	X			
Medical History/Concomitant Medications	X	X	X	X
Habitual Contact Lens Information	X			
Inclusion/Exclusion Criteria	X			
Adverse event review		X	X	X
Subjective Sphero- Cylindrical Refraction	X			
Visual acuity with refraction	X			
Corneal topography	X			
Tear meniscus height			X	X
Non-invasive tear break- up time			X	X
Tear film osmolarity			X	X
Tear sample collection (and storage)			X	X
Slit Lamp biomicroscopy	X	X	X	X
Compliance		X		X
Continuance	X	X	X	
Lid margin staining and photography			X	X
Lens application	X		X	
Comfort scores	X	X	X	X

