**Clinical Study Protocol**  
**Johnson & Johnson Vision Care, Inc.**

Visit 4: Treatment 2 Follow-Up (after 14h)		
Step	Procedure	Details
		
this point and a Final Evaluation form should be completed.
 
All subjects are eligible to repeat Visits 3 and 4 of Part 1 on ONE more occasion on a different day if any problems with the lens wear occur between Part 1, Visits 3 and 4. If such problems do occur, Visit 3 will also need to be repeated.

4.3	Subject Reported Ocular Symptoms	Record subject reported ocular symptoms.
4.4	Subjective comfort	Subjective comfort scores for each lens (OD and OS) separately using a vertical VAS scale will be recorded.
4.5	LogMAR visual acuity & over-refraction	Distance high contrast visual acuity will be measured for each eye and binocularly as well as after an over-refraction. The acuity will be recorded to the nearest letter.
4.6	Lens fitting and surface assessment	
Lens fit will be measured using a slit lamp graticule for the following:
 
Coverage:            Nasal coverage            Temporal Coverage            Inferior Coverage            Superior Coverage
 
Centration:            Horizontal centration (by auto calculation)            Vertical centration (by auto calculation)
 
Movement in primary position
 
The lens surface will be recorded according to the following integer scales: lens deposits (0-2), deposit degree (0-4), lens debris (0-4) and lens wettability (0-4).

4.7	Tear height meniscus	
The OD lower tear meniscus will be imaged using the OCT.
 
Three images will be taken.

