**Clinical Study Protocol**  
**Johnson & Johnson Vision Care, Inc.**

Visit 7: Treatment 4 Lens Fitting and dispensing		
Step	Procedure	Details
7.15	Continuance	
The lens fit and VA must be acceptable in order for a subject to continue on the study.
 
Minimum acceptable logMAR VA is 0.18 binocularly
 
If subject is deemed not to be able to continue, proceed to Final Evaluation and complete all forms.

7.16	Tear meniscus height	
The OD lower tear meniscus will be imaged using the OCT.
 
Three images will be taken.

7.17	Non-invasive tear break-up time	
OD tear film break up time will be measured using the Medmont topographer
 
Three measurements will be undertaken.

7.18	Tear film osmolarity	
OD osmolarity measured using the Tearlab.
 
Two measurements will be undertaken.

7.19	Tear sample collection	
OD; 2<math>\mu</math>l tear sample will be collected using a glass capillary tube before application of any dyes to the ocular surface.
 
Tears will be collected over a maximum period of 15 minutes.

7.20	LogMAR visual acuity	
Distance high contrast visual acuity will be measured for each eye and binocularly. The acuity will be recorded to the nearest letter for each eye.

7.21	Lens wear instructions	
The subject will be instructed to wear the lenses for the rest of the day and not to remove the lenses before the next visit.

7.22	End of Visit 7 and Instructions	
Subject discharged and asked to return 14 <math>\pm</math> 2 hours later (from the time of lens application).

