**Clinical Study Protocol**  
**Johnson & Johnson Vision Care, Inc.**

Visit 8: Treatment 4 Follow-Up (after 14± 2 hours)			
Step	Procedure	Details	
8.1	Adverse Events and Concomitant Medications Review	Review any changes to the subject's medical history or concomitant medications from the previous study visit. Record any changes, and any adverse events.	
8.2	Compliance	
Questions regarding the subject's contact lens wear since the previous visit. The number of hours of lens wear as well as the number of comfortable hours of lens wear will be recorded.
 
N.B. Subjects should not have removed the lenses since the previous visit.
 
If subjects have had to remove one or both lenses, the investigator should stop the visit at this point and a Final Evaluation form should be completed.
 
All subjects are eligible to repeat Visits 7 and 8 of Part 2 on ONE more occasion on a different day if any problems with the lens wear occur between Part 2, Visits 7 and 8. If such problems do occur, Visit 7 will also need to be repeated.
	
8.3	Subject Reported Ocular Symptoms	Record subject reported ocular symptoms.	
8.4	Subjective comfort	Subjective comfort scores for each lens (OD and OS) separately using a vertical VAS scale will be recorded.	
8.5	LogMAR visual acuity & over-refraction	Distance high contrast visual acuity will be measured for each eye and binocularly as well as after an over-refraction.	Eurolens Research SOP # 12a
8.6	Lens fitting and surface assessment	Lens fit will be measured using a slit lamp graticule for the following:	Eurolens Research SOP # 24

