### 8.2. Withdrawal/Discontinuation from the Study

A subject will be withdrawn from the study for any of the following reasons:

- Subject death during the study period
- Subject withdrawal of consent
- Subject not compliant to protocol including use of non-study lenses or not reaching the required wear times
- Subject lost to follow-up
- Subject no longer meets eligibility criteria (e.g. the subject becomes pregnant)
- Subject develops significant or serious adverse events causing discontinuation of study lens wear (more than 7 days)
- Subjects who have experienced a Corneal Infiltrative Event (CIE)
- Investigator's clinical judgment regarding the subject safety reasons (that it is in the best interest of the subject to stop treatment)
- Subject missed a study visit

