#### ADVERSE REACTIONS

Potentially serious complications are usually accompanied by one or more of the following signs or symptoms:

- Foreign body sensation
- Excessive watering or other unusual eye secretions including mucopurulent discharge
- Redness of the eyes
- Photophobia (sensitivity to light)
- Burning, stinging, itching or other pain associated with the eyes
- Comfort is less compared to when the lens was first placed on eye
- Poor visual acuity (reduced sharpness of vision)
- Blurred vision, rainbows or halos around objects
- Feeling of dryness

If any of the previous signs or symptoms occur:

- The patient should IMMEDIATELY REMOVE THE LENS(ES). If the discomfort or problem stops, the patient should discard the lens and replace it with a new one. IF THE PROBLEM CONTINUES AFTER INSERTING A NEW LENS, THE PATIENT SHOULD IMMEDIATELY REMOVE THE LENS(ES) AND CONTACT AN EYE CARE PROFESSIONAL AT ONCE.
- Patients should be informed that a serious condition such as corneal ulcer, infection, corneal vascularization, or iritis may be present and may progress rapidly. Less serious reactions such as abrasions, infiltrates and bacterial conjunctivitis must be managed and treated early to avoid more serious complications. Additionally, contact lens wear may be associated with ocular changes which require consideration of discontinuation or restriction of wear. These include but are not limited to local or generalized corneal edema, epithelial microcysts, epithelial staining, infiltrates, neovascularization, endothelial polymegathism, tarsal papillary changes, conjunctival injection or iritis.

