**THE PATIENT SHOULD BE INSTRUCTED TO IMMEDIATELY REMOVE THE LENSES AND PROMPTLY CONTACT THE EYE CARE PROFESSIONAL.**

- When prescribed for daily wear, patients should be instructed not to wear lenses while sleeping. Clinical studies have shown that the risk of serious adverse reactions is increased when lenses are worn overnight, and that the risk of ulcerative keratitis is greater for

CR

J

TIAL

extended wear contact lens users than for daily wear users.

- Studies have shown that contact lens wearers who are smokers have a higher incidence of adverse reactions than nonsmokers.
- Problems with contact lenses or lens care products could result in serious injury to the eye. Patients should be cautioned that proper use and care of contact lenses and lens care products are essential for the safe use of these products.
- The overall risk of ulcerative keratitis may be reduced by carefully following directions for lens care.

 New England Journal of Medicine, September 21, 1989; 321 (12), pp. 773-783

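### Steps 3.21 and 7.21 forbid lens removal for 14 ± 2 hours with no exception, against the removal warnings in both Appendix C inserts, and what follows an early removal is not clearly stated

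*Combined protocol and SAP*

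**What the plan says.** **Instruction on the study day.** Section 7.2, step 3.21 (Part 1) and step 7.21 (Part 2) tell the subject to "wear the lenses for the rest of the day and not to remove the lenses before the next visit". Table 3 sets that next visit at "14 ± 2 hours from Visit 3", with the same interval from Visit 7 to Visit 8.

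**Labelling supplied with the protocol.** The Acuvue Oasys 1-Day insert, after listing eye discomfort, redness and vision changes, says "THE PATIENT SHOULD BE INSTRUCTED TO IMMEDIATELY REMOVE THE LENSES AND PROMPTLY CONTACT THE EYE CARE PROFESSIONAL". The Dailies AquaComfort Plus insert gives the same direction under Warnings. Its Adverse Reactions section includes "Comfort is less compared to when the lens was first placed on eye" among the signs that call for immediate removal; the Acuvue insert has an equivalent item. Section 1.2 states that the lenses are used as indicated, and Section 1.4 names the inserts as the fullest source of risk information.

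**After a removal.** Steps 4.2 and 8.2 record hours of wear and comfortable hours, then say "If subjects have had to remove one or both lenses, the investigator should stop the visit at this point and a Final Evaluation form" is to be filled in. The same steps add "All subjects are eligible to repeat Visits 3 and 4 of Part 1 on" one further day (Visits 7 and 8 in Part 2). Section 8.2 lists, among reasons a subject will be withdrawn, "Subject not compliant to protocol including use of non-study lenses or not reaching the required wear times", and discontinued subjects are replaced.

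**The concern.** Reduced comfort late in the day is a foreseeable event in this study. About half of the continuing subjects have a CLDEQ-8 score of 20 or more after two weeks in the Part 1 lens, and comfort at 14 hours is a secondary endpoint. Such a subject holds two directions that cannot both be followed: keep the lenses in until the visit, or take them out at once. The first matter at stake is therefore a consistent safety instruction.

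The second is data. The stop at step 4.2 or 8.2 comes before the 14-hour comfort score and before staining, NIBUT, TMH and osmolarity. If removals are commoner among symptomatic subjects, the 14-hour comparison rests more on those who tolerated the day. The plan has no display that would show this. Missing values are not imputed, the multiple-imputation sensitivity analysis depends on overall dropout above 15% (Section 14.9), and the per-protocol set contains only subjects who completed all visits (Section 14.3).

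**Working it through.** **1. Passages side by side**

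| Place | Direction |
|---|---|
| Steps 3.21, 7.21 | No removal before the next visit; no exception |
| Appendix C, both inserts | Instruct removal at once for discomfort, redness, vision change |
| Section 1.2 | Lenses used as indicated |
| Section 1.4 | Subjects trained on discomfort; content not given, no link to 3.21 or 7.21 |
| Steps 4.2, 8.2 | Removal foreseen; visit stops; Final Evaluation form; one repeat of the paired visits |
| Final Evaluation (Section 7.2) | Done after the last visit, or on discontinuation or termination |
| Section 8.2 | Unmet wear time is a reason for withdrawal |

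The window is 14 − 2 = 12 to 14 + 2 = 16 hours, on two study days per subject. The symptomatic share is 27/54 = 50%.

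**2. The plan's own power figures**

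The formula is a two-sample t test with 27 per stratum, 52 degrees of freedom, one-sided 5% and critical value 1.675. The noncentrality is Δ / (σ√(2/27)).

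- TMH, Δ = 0.04, σ = 0.06 (Table 12): 0.04/(0.06 × 0.2722) = 2.449, power 78.0%. The table states 78%.
- LMS, Δ = 0.35, σ = 0.5 (Table 10): power 81.4%. The table states 81%.

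**3. What an assumed attenuation would do (TMH cell)**

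- Difference 10% smaller: noncentrality 2.205, power 70.2%.
- Difference 20% smaller: noncentrality 1.960, power 61.4%.

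Nothing in the documents supports 10% or 20%.

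**4. What loss would be needed to reach that**

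Assume that the fraction f of symptomatic subjects most prone to remove is lost, that proneness correlates ρ with the measure in the hypothesised direction, that replacement restores n to 27, and that σ is unchanged. The stratum mean then shifts by ρ·φ(z)/(1 − f) SD, where z is the upper-f normal quantile.

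| Lost of 27 | φ(z)/(1 − f) | ρ | Shift (SD) | Shrinkage of 0.04 | Power |
|---|---|---|---|---|---|
| 1 | 0.0809/(26/27) = 0.084 | 0.3 | 0.025 | 3.8% | 75% |
| 1 | 0.084 | 0.5 | 0.042 | 6.3% | 73% |
| 4 | 0.2312/(23/27) = 0.271 | 0.3 | 0.081 | 12.2% | 68% |
| 4 | 0.271 | 0.5 | 0.136 | 20.4% | 61% |

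Attenuation of 10–20% therefore needs about 4 of 27 permanently lost (14.8%).

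**5. What the documents say about loss**

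Table 4 reports an earlier study in Dailies AquaComfort Plus: 42 enrolled and 25 + 16 = 41 completed. Loss was 1/42 = 2.4% (exact 95% interval 0.1% to 12.6%). If that one subject was symptomatic, the stratum figure is 1/17 = 5.9%. Neither the stratum nor the cause is given.

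**6. Whether the plan would notice**

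Taking 54 as the denominator (an assumption), 15% is 8.1 subjects. Eight losses (14.8%) would not trigger the sensitivity analysis even if all were symptomatic (8/27 = 29.6%).

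**The case against.** The strongest reply is that steps 3.21 and 7.21 are not the only instruction subjects receive. Section 1.4 promises training on discomfort, including what to do outside clinic hours. A patient instruction guide is issued at Visits 1 and 5, unscheduled visits are provided for, and steps 4.2/8.2 plainly expect that some subjects will have needed to remove a lens. The guide's text is supplied separately, so what subjects are actually told cannot be seen. This softens the conflict without resolving it: nothing qualifies the instruction given at the start of the study day.

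Several stronger readings are tempting and are not supported:

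- **That removal forfeits the 14-hour data.** It does so for that day only; one repeat of the paired visits is open to every subject.
- **That the strata are pulled together.** This assumes discomfort tracks each measure in the hypothesised direction, which is the study's own secondary question. For osmolarity the earlier 14-hour means run the other way (Table 8: 288.41 symptomatic, 301.38 asymptomatic, difference −12.97).
- **That power falls to 61–70%.** The arithmetic is right, but it needs a loss about six times the earlier rate (14.8/2.4).
- **That the stratum is selected for a fall in comfort during the day.** The questionnaire's content is not shown, only its cut-offs.
- **That removal has three incompatible outcomes.** They can mostly be read as a sequence: stop, repeat once, then withdraw. What stands is narrower. A Final Evaluation belongs to the last visit or to discontinuation, yet a repeat may follow it, and unmet wear time is separately listed as a reason for withdrawal.

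**Conclusion.** The conflict of instructions holds on the text and should be fixed. It applies to all continuing subjects on two study days each, and matters most for the roughly 27 in the symptomatic stratum. It does not rest on any assumed removal rate. The unclear status of a subject after an early removal also holds, as a matter of wording that sites could apply differently.

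The statistical consequence is weaker. Loss may fall more on the symptomatic stratum, and a successful repeat keeps only a day that was tolerated, but the size and direction of any bias are unknown. The earlier study suggests that few are lost, though its study number is redacted, so it cannot be established whether the same removal rule applied. Only the four 14-hour measures are directly exposed. White cells are imaged at Visits 2 and 6, although a non-completer also leaves the per-protocol set. The power figures above are illustrations, not estimates. Severity: should-fix.

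**What to change.** 1. Reconcile steps 3.21 and 7.21 with Section 1.4 and the Appendix C removal warnings, so that subjects receive one consistent instruction. Which rule to adopt is for the sponsor and investigator.
2. Reconcile steps 4.2 and 8.2 with the Final Evaluation section and Section 8.2, so that it is clear whether participation ends when a repeat is still available.
3. Add the reason for early removal to the hours of wear already recorded at steps 4.2/8.2. The Final Evaluation asks for a reason only on discontinuation, so it may miss a subject who goes on to repeat. A comfort score for the moment of removal is not recommended: taken at the later visit, it would be recall.
4. Tabulate early removals, repeats and replacements by stratum, for Part 1 and Part 2.

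The cost is minor amendment wording, one CRF field and one summary table. No extra subjects, visits or procedures are needed.
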